intubation attempts. Tracheal ultrasonography was used in ten studies and lung ultrasonography was used in four studies, two studies used both tracheal and lung ultrasonography to confirm endotracheal tube placement. Seven studies used capnography or ETCO₂ detectors as criterion standard of tracheal intubation whereas the remaining studies used direct laryngoscopy, chest auscultation, or chest radiography. For detection of oesophageal intubation, the pooled sensitivity of ultrasonography was 0.93 (95% CI: 0.86–0.96) and the specificity was 0.97 (95% CI: 0.95–0.98). The positive and negative likelihood ratios were 26.98 (95% CI: 19.32–37.66) and 0.08 (95% CI: 0.04–0.15) respectively. A hierarchical summary receiver operating characteristic curve that plots sensitivity versus specificity was constructed and the area under the curve was calculated to be 0.97 (0.95–0.98). In tracheal ultrasonography, attending physicians demonstrated superior sensitivity (0.98, 95% CI: 0.96–0.99) when compared to resident physicians (0.92, 95% CI: 0.78–0.96). Tracheal ultrasonography performed in the emergency had a lower sensitivity (0.88, 95% CI: 0.76–0.94) in comparison to other settings. Tracheal ultrasonography performed in real-time was associated with superior sensitivity (0.94, 95% CI: 0.86–0.98) than that performed post-intubation in static manner (0.91, 95% CI: 0.70–0.98). They concluded that ultrasonography had high diagnostic value for identifying oesophageal intubation. They recommended ultrasonography be used as a valuable adjunct in endotracheal intubation confirmation, especially in situations where capnography may be unreliable.⁶

A systematic review and meta-analysis was also done by Das et al²¹ in 2015 to evaluate the diagnostic accuracy of transtracheal ultrasound in detecting endotracheal intubation. Eleven studies and 969 intubations were included in the final analysis.

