Eight studies and 713 intubations had been performed in emergency situations and the others were carried out in elective situations. Transtracheal ultrasonography's pooled sensitivity and specificity with 95% confidence interval (CI) were 0.98 (95% CI: 0.97 - 0.99) and 0.98 (95% CI: 0.95 - 0.99) respectively. In emergency scenarios, transtracheal ultrasonography showed an aggregate sensitivity and specificity of 0.98 (95% CI: 0.97 - 0.99) and 0.94 (95% CI: 0.86 - 0.98) respectively. Transtracheal ultrasound was concluded to be a useful tool to confirm endotracheal intubation. They recommended that transtracheal ultrasonography could be used as a preliminary test for endotracheal intubation before final confirmation by capnography.²¹

Karacabey et al²⁷ did a study to evaluate accuracy and speed of ultrasonography for confirming endotracheal tube placement by tracheal ultrasound and lung sliding. They also observed the degree of agreement of ultrasonography when used for endotracheal tube confirmation along with capnography as the standard method. The study was a prospective, single-centre, observational study conducted in the emergency department of a tertiary care hospital. Patients who had emergency intubation because of respiratory failure, cardiac arrest or severe trauma were included. A total of 115 patients were included in the study. Among 115 patients, 30 were cardiac arrest patients. The overall accuracy of the ultrasonography in their study was 97.18% (95% CI: 90.19% – 99.66%), and the value of kappa was 0.869 (95% CI: 0.77 – 0.96) indicating a high degree of agreement between ultrasonography and capnography. Ultrasonography took significantly less time than capnography, mean of 5.8 seconds versus 11.7 seconds respectively.²⁷

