Duration of study: 6 months. The study was conducted at MCVTC from January 17, 2017 to April 14, 2017. It was continued at TUTH from April 15, 2017 to July 14, 2017.

Sampling Method: Non-probability sampling.

Sample size: Total 95 patients were taken for analysis.

The formula for sample size with $(1 - \alpha)\%$ confidence level and with maximum margin error of estimate of “d” for constructing confidence interval of true value of sensitivity or specificity using normal approximation is given as follows³⁵:

$$n = \frac{Z_{\frac{\alpha}{2}}^2 \hat{P}(1 - \hat{P})}{d^2}$$

Where \hat{P} is pre-determined value of sensitivity or specificity that is ascertained by previous published data or clinician experience or judgment.³⁵

For $\alpha = 0.05$, $Z_{\alpha/2}$ is inserted by 1.96.^{35,36}

Excerpted from the meta-analysis done by Chou et al⁶ where they found the sensitivity and specificity of suprasternal transtracheal ultrasound for endotracheal tube confirmation to be 0.98 and 0.94 respectively, the specificity value for \hat{P} in the equation was taken. Hence setting margin of error “d” at 5%, we could equate to:

$$n = 1.96^2 \times 0.94 \times 0.06 / 0.05^2 = 86.66$$

Adjusting for 10% drop outs and defaulters, a sample size of 95 was thus taken.

Inclusion criteria:

ASA I and II patients of both sexes above 16 years of age undergoing general anaesthesia with endotracheal tube placement.

Exclusion criteria:

- Patient refusal
- ASA physical status III and above
- History of prior difficult bag and mask ventilation or difficult intubation
- History of prior oro-nasal or neck injuries, burns or scars
- Active oral, pharyngeal or tracheal infection or inflammatory changes
- Anticipated difficult airway or difficult intubation during preanaesthetic examination, with Mallampati grades II and above
- Lung parenchymal and pleural diseases. Examples: asthma, COPD, bronchiectasis, reactive lung diseases, pneumonia, tuberculosis, pleural effusion, pneumothorax, lung or pleural malignancy etc.
- Emergency surgery

- Patients with known oesophageal pathology. Examples: oesophageal carcinoma, stricture, tracheoesophageal fistula etc.
- Full stomach or patients at risk of aspiration, e.g. pregnancy
- Patients with a nasogastric tube in situ
- NYHA grade 2 and above

Materials and Methods

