Hence these descriptive variables did not affect the outcome of the study. These variables reflect the demographic profile of the patients served at the academic centres of IOM in Maharajgunj and provide validity to the study. This data could help as reference for researchers who might carry out similar studies in the same centres in future.

Analytical Statistics

The incidence of oesophageal intubation was 11.57% in this study. Reported incidence of oesophageal intubations during elective intubation is less than 2%.^{12,39}

The incidence of oesophageal intubation increases up to 6 - 16 % during in-hospital emergency intubations.^{29,30,39,40}

Ultrasonography

In this study, the sensitivity, specificity, positive predictive value and negative predictive value (with their corresponding 95% confidence intervals) of ultrasonography were calculated to be 97.62% (91.66% - 99.71%), 90.91% (58.72% - 99.77%), 98.80% (92.67% - 99.81%) and 83.33% (55.66% - 95.22%) respectively.

The sensitivity of ultrasonography in this study is comparable to sensitivity reported in the meta-analyses done by Das et al²¹ and Chou et al⁶, which were 98% and 93% respectively. The specificity was 90.91% in this study, which is slightly lower compared to the above mentioned meta-analyses where specificity ranges from 97 to 98%.^{6,21} But the 95% confidence interval of specificity in this study extends from 58.72 to 99.77% which covers the reported specificity 97 to 98% in these meta-analyses. Thus the calculated pretest probabilities of ultrasonography in this study were not different from those reported in literature.

The PPV and NPV of ultrasonography calculated in this study were 98.8% and 83.33% respectively. The PPV of ultrasonography in this study is similar to that found by Adi et al³⁰, Chou et al²⁸, Chintamani et al³⁴ and Nasreen et al³³: the reported PPV ranges from 98 to 100% in these studies. The NPV of ultrasonography has been reported to be: 62.5% by Chintamani et al³⁴, 75% by Adi et al³⁰, 94% by Chou et al²⁸, and 96.77% by Nasreen et al³³. The 95% confidence interval of NPV of ultrasonography in this study was (55.66%- 95.22%), which is comparable to the NPV found by the above mentioned studies.

Ultrasonography had an accuracy of 96.84% in endotracheal tube confirmation in this study. Similar accuracy ranging from 97 to 98% had also been found by previous researchers.^{28,30,33}

There are various ways of using ultrasonography for endotracheal tube confirmation.

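### The planning specificity of 0.94 is not what the document reports for its credited meta-analysis, and the Discussion benchmarks against that source with sensitivity and specificity reversed

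*Combined protocol and SAP*

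**What the plan says.** **Sample size (Methodology).** The plan uses a normal-approximation precision formula for one proportion. It credits the first meta-analysis (reference 6) with finding "the sensitivity and specificity of suprasternal transtracheal ultrasound for endotracheal tube confirmation to be 0.98 and 0.94 respectively", takes the specificity as the planning value, sets a 5% margin and obtains 86.66. It then states: "Adjusting for 10% drop outs and defaulters, a sample size of 95 was thus taken".

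**Literature Review, first meta-analysis (reference 6).** "For detection of oesophageal intubation, the pooled sensitivity of ultrasonography was 0.93", and the specificity in the same sentence is 0.97. Ten of its studies used tracheal and four used lung ultrasound, with two using both. The same paragraph gives a sensitivity of 0.94 (95% CI 0.86 to 0.98) for real-time tracheal scanning and 0.98 for attending physicians.

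**Literature Review, second meta-analysis (reference 21).** This one concerns detection of endotracheal intubation. Overall sensitivity and specificity are both 0.98. "In emergency scenarios, transtracheal ultrasonography showed an aggregate sensitivity and specificity of 0.98" and 0.94 respectively.

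**Operational Definitions and the formulas after Table 1.** Ultrasound positive means trachea, and specificity is TN/(TN+FP). Specificity is therefore the share of oesophageal tubes that ultrasound calls oesophageal.

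**Discussion, Analytical Statistics, Ultrasonography.** The trial's sensitivity is set against 98% (second source) and 93% (first source). Its specificity of 90.91% is described as a value "which is slightly lower compared to the above mentioned meta-analyses where specificity ranges from 97 to 98" per cent.

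**The concern.** The planning proportion is the only literature-derived input to the sample size. The sample-size section and the Literature Review give different figures for the same source. The figures used match another source, in an emergency setting, while this trial enrols elective patients and lists emergency surgery as an exclusion. A reader who follows the citation cannot arrive at 87.

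The second problem is orientation. The first meta-analysis treats oesophageal intubation as the target, whereas this trial treats tracheal intubation as the positive result. The first source's sensitivity therefore corresponds to this trial's specificity, and the reverse. The Discussion does not make the switch, so for that source it compares unlike quantities. Its statement that the trial agrees with the literature rests partly on that comparison.

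**Working it through.** **Inputs.** From the sample-size section: *z* = 1.96, *d* = 0.05, planning value 0.94, stated result 86.66, 10% drop-out, final size 95. From the Literature Review: 0.93/0.97 and real-time 0.94 (first source), 0.98/0.98 overall and 0.98/0.94 emergency (second source). From Results: 11 oesophageal intubations among 95.

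**1. The plan's own figure.** n = 1.96² × P(1 − P) / *d*².

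P = 0.94: 3.8416 × 0.94 × 0.06 / 0.0025 = 86.67, which rounds up to 87. The stated 86.66 reproduces. Adding 10% gives 86.67 × 1.10 = 95.3, stated as 95. Dividing by 0.90 gives 96.3. That difference is rounding and convention, and I make nothing of it.

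**2. Orientation.** With trachea as positive, the first source's pooled 0.93 (oesophageal tubes correctly called) is a specificity, and its 0.97 is a sensitivity. The second source already has this trial's orientation. I assume that the first source's subgroup sensitivities share the orientation of its pooled result, because the Literature Review does not restate it for them.

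**3. The formula under each candidate specificity.**

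| Source of P, in this trial's orientation | P | n | Rounded up |
|---|---|---|---|
| First source, pooled, flipped | 0.93 | 3.8416 × 0.0651 / 0.0025 = 100.04 | 101 |
| First source, real-time tracheal, flipped | 0.94 | 86.67 | 87 |
| Second source, emergency subset | 0.94 | 86.67 | 87 |
| First source, pooled, not flipped | 0.97 | 3.8416 × 0.0291 / 0.0025 = 44.72 | 45 |
| Second source, overall | 0.98 | 3.8416 × 0.0196 / 0.0025 = 30.12 | 31 |

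Only the two rows with 0.94 return the plan's number, and the sample-size section names neither.

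**4. What the formula's n counts.** The specificity denominator is TN + FP, here 11. The half-width is 1.96 × √(P(1 − P)/11):

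- P = 0.94: 1.96 × √(0.0564/11) = 0.140
- P = 0.93: 1.96 × √(0.0651/11) = 0.151

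Putting all 95 patients into the same expression gives 0.048 and 0.051, but these do not describe the precision of specificity.

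**5. Discussion benchmarks after flipping the first source.**

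| | Trial (95% CI) | Benchmark as written | Benchmark, common orientation |
|---|---|---|---|
| Sensitivity (trachea) | 97.62% (91.66 to 99.71) | 93% and 98% | 97% and 98% |
| Specificity (oesophagus) | 90.91% (58.72 to 99.77) | 97% and 98% | 93% and 98% |

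The gap between observed specificity and the nearest benchmark falls from 97 − 90.91 = 6.09 points to 93 − 90.91 = 2.09 points. Both confidence intervals still cover the corrected ranges.

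**The case against.** The best defence is that 0.94 may be right. The Literature Review gives 0.94 from the first source for real-time tracheal scanning, and the Discussion repeats it. Flipped, that is a specificity of 0.94 for the technique closest to this trial's, whereas the pooled 0.93 mixes tracheal and lung ultrasound. The value also lies inside that source's pooled interval of 0.86 to 0.96, and the plan allows the planning value to come from clinical judgement. This stands: 0.94 is a defensible choice and n can remain 87.

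It does not rescue the text. The sample-size section does not say that 0.94 is a real-time subgroup figure or a flipped sensitivity, and it pairs it with a sensitivity of 0.98. In the summary of the first source, 0.98 is another sensitivity, for attending physicians. Two sensitivities from different subgroups are not a sensitivity and specificity pair. What the source itself reports for suprasternal scanning cannot be settled from these documents, but the sections still have to agree.

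A reader might infer that the trial needed 101 patients and fell short with 95, achieving ±5.13% instead of ±5%. The documents do not support that. The 101 follows from one of two candidate values in the same source. Both the comparison with 95 and the 5.13% margin count all patients, although specificity is estimated only in oesophageal intubations. The far wider half-width with 11 such cases is a separate matter that arises whichever value is used.

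A reader might also infer that the Discussion's claim of consistency with the literature collapses. It does not: the agreement is closer once the figures are aligned.

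**Conclusion.** The concern holds as an error of attribution and orientation. The stated arithmetic reproduces. The pair credited to the first meta-analysis is not what the Literature Review reports for it, and the labelled pair belongs to the emergency subset of the second.

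In this trial's orientation the first source supports 0.93 pooled (n = 101) or 0.94 real-time tracheal (n = 87), the latter on the assumption that the subgroup shares the pooled orientation. The effect on planning is one point in P and 14 in the formula's n, and it disappears if the real-time subgroup is named as the source.

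In the Discussion, the literature range of 97 to 98% for specificity is wrong for the first source and should be 93 to 98%. Observed specificity is still below that range as a point estimate, and the overall conclusion of consistency is unchanged. The trial's own accuracy estimates are unaffected.

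**What to change.** - **Sample size.** Reconcile this section with the two Literature Review summaries. State the true source, subgroup and orientation of 0.94: either the first source's real-time tracheal sensitivity for oesophageal detection, flipped, or the second source's emergency subset, acknowledging that this trial is elective. Correct or remove the accompanying 0.98 so that the two figures form a genuine pair.
- **Show both values.** Give the formula's n under the pooled 0.93 (101) beside 0.94 (87), and say that it counts oesophageal intubations. Do not report ±5.13% as the precision achieved. With 11 oesophageal intubations the formula's half-width is about ±14 to ±15 points.
- **Discussion.** Swap the first source's figures, so that tracheal sensitivity is compared with 97 to 98% and oesophageal specificity with 93 to 98%. Revise the sentence that places specificity below a literature range of 97 to 98%.

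The cost is a text correction in two sections. It needs no new data, no further patients and no re-analysis.

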5. Researcher: noted down the time taken for confirmation by both methods. Also inspected for changes in vitals that would exclude the participant out of the study.

Inside the operating room the ultrasound machine was kept on the left hand side and in line with pelvis of the patient. The ultrasound operator was on the right hand side of the patient and in line with patient's xiphisternum. The blinding was done such that

the person reading capnogram would face away from the ultrasound machine, and the ultrasound operator would be facing away from the capnograph monitor.

Patient was placed supine comfortably in the operating table. Continuous ECG and SPO₂ monitoring, 5 minute interval NIBP monitoring or continuous invasive blood pressure monitoring when available was done. A running intravenous drip of crystalloid solution; Ringer's Lactate, Normal saline or Plasmalyte as required was started. Injection Fentanyl 2 microgram per kg was given intravenously. Then Injection Propofol 2 milligram per kg was given intravenously in TUTH and non-cardiac surgery patients in MCVTC, and Injection Etomidate 0.3mg per kg intravenously was given to cardiac surgery patients in MCVTC for induction. Induction of anaesthesia was complete after patient became unresponsive with central mid-dilated pupil and absence of eye lash reflex.

Manual bag and mask ventilation adequacy was then checked. Injection Vecuronium 0.1 milligram per kg was given intravenously, and the stopwatch was started. Manual bag and mask ventilation was continued by the primary intubating resident and assisted by the supervising anaesthesia faculty as needed.

High frequency linear ultrasound probe, 9-13 Megahertz, was placed transversely just above the suprasternal notch. The probe was shifted slightly cranially or caudally as needed to obtain the best visualization of trachea and oesophagus in the same image.

After 5 minutes of injecting Vecuronium, the researcher reset his stopwatch and announced "start" loudly (start point). Laryngoscopy and tracheal intubation was done by the anaesthesia resident. The ultrasound operator held the probe in the appropriate place as previously determined. If the position of the probe obstructed laryngoscopy,

the probe was shifted caudally and tilted slightly cranially. The study was continued only if the latter ultrasound image could also visualize both trachea and oesophagus.

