After intubation, the anaesthesia machine which was preset in volume control mode with tidal volume of 6ml/kg, respiratory rate of 26 breaths per minute (as used by Pfeiffer et al³¹ in their study), PEEP zero and inspiration:expiration ratio of 1:2; was then attached to the endotracheal tube via the anaesthesia machine circuit with ETCO₂ probe connected at the angle piece of the patient end of the circuit.

The ultrasound operator announced loudly as either “ultrasound positive” for tracheal intubation result, or “ultrasound negative” for oesophageal intubation result. The researcher noted down the time in the data entry proforma sheet (end point for ultrasonography).

The next anaesthesia resident (or anaesthesia assistant) meanwhile watched over the capnogram in the monitor. After 6 mechanical ventilations, he announced loudly as “capnograph positive” for tracheal intubation result, or “capnograph negative” for oesophageal intubation result. The researcher noted down the time in data entry proforma sheet (end point for capnography).

The supervising anaesthesia faculty then auscultated the chest in 5 areas in the order: right supramammary – left supramammary - left axillary – right axillary – epigastrium. The ultrasound operator performed bilateral lung ultrasound in second intercostal spaces in the mid-clavicular line and observed for lung sliding. The final endotracheal tube position in trachea was confirmed when there was presence of bilateral air entry on auscultation and lung sliding on ultrasound. In case of only unilateral air entry and unilateral lung sliding, the endotracheal tube was readjusted

for endobronchial intubation and reconfirmed again; the subject was not excluded from the study in the event of endobronchial intubation.

If there was absence of breath sounds with absence of lung sliding and bar-code sign²⁰ in the ultrasound in bilateral chest regions, reconfirmation further was done by the supervising anaesthesia faculty by performing repeat laryngoscopy and visualizing the position of endotracheal tube in relation to the vocal cords. This repeat reconfirmation was done because post-intubation bronchospasm or mucous plugging could also present with similar auscultation and lung ultrasound finding and thus negate the validity of the study. The supervising anaesthesia faculty would then reintubate himself if tube position in the oesophagus was seen during repeat laryngoscopy. The second intubation was not accounted for in this study.

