Participants were also excluded if there was:

- Unanticipated difficult bag and mask ventilation
- Unanticipated difficult intubation or CL grade 3 and 4 cases, use of bougie for intubation.
- Fall in Spo₂ (< 90%) before endotracheal tube position confirmation
- Bradycardia (heart rate < 40 beats/min) or hypotension (mean arterial pressure < 60 mm of Hg, systolic blood pressure < 80 mm of Hg) during or prior to intubation
- Tachycardia more than 120 bpm or blood pressure more than 180 mm Hg systolic or 110 mm Hg diastolic during or prior to intubation

There were 36 participants enrolled at MCVTC, out of which 5 of the participants had to be excluded out of the study. One had unanticipated difficult intubation, and the other four had hypotension after induction of anaesthesia. There were 67 participants

enrolled at TUTH, out of which 3 participants had to be excluded out of the study. Two subjects had hypotension after induction of anaesthesia. The other one had to be excluded because the ultrasound machine went into hung state. Thus there were 31 subjects from MCVTC and 64 subjects from TUTH. Data collection was terminated once the sample size of 95 was met. Different individuals operated ultrasound on the subjects in this study. Flow diagram of the study is shown in figure 8.

Operational Definitions

Ultrasound positive: meant ultrasound detected tracheal intubation. There was fluttering and movement inside the tracheal acoustic shadow as the endotracheal tube was passed, and by the completion of intubation there was only one comet tail appearing acoustic shadow. Color Doppler ray showed color change inside the acoustic shadow on shaking the endotracheal tube.

Ultrasound negative: meant ultrasound detected oesophageal intubation. There was fluttering and increase in echogenicity in the region of oesophagus as the endotracheal tube was passed. By the completion of intubation, there were two comet tail appearing acoustic shadows, “double-tract sign”. Color Doppler ray was seen outside the trachea on shaking the endotracheal tube.

Capnograph positive: meant capnogram showed regular normal shaped waveforms after 6 ventilations. The outcome was tracheal intubation.

Capnograph negative: meant oesophageal intubation. The capnogram had no waveforms or irregular, bizarre or non-uniform shaped waveforms after 6 ventilations.

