< 0.1	Large change in likelihood (or in other words high probability of any individual having a negative result on using the diagnostic test).
0.1 – 0.2	Moderate change in likelihood.
0.2 – 0.5	Small change in likelihood.
1	No change.

Data collection and management

The Pre-anaesthetic (PAC) form of the Department of Anaesthesiology, MMC, IOM; (Appendix A) was used to evaluate patients for inclusion into the study. All participants' data such as gender, age, ethnicity, diagnosis, BMI, weight, ASA status, medical comorbidities, airway examination was collected on data entry proforma sheet (Appendix C). The proforma sheet also recorded the baseline vitals and the vitals after induction of anaesthesia and after intubation. The results for ultrasonography and capnography, the respective time taken to obtain the results were recorded in the proforma sheet.

Data entry was done into Microsoft excel 2010. (Appendix E)

Statistical Analysis

Descriptive variables were expressed as mean \pm standard deviation, median, range, interquartile range, frequency, percentage and proportion. The calculations were done in Microsoft excel 2010.

The sensitivity, specificity, positive and negative predictive values, accuracy, along with their confidence intervals and likelihood ratios for positive and negative results were calculated by defining the respective mathematical functions into Microsoft excel 2010.

The mean and median times along with the interquartile range and standard deviations, taken for confirmation by capnography and ultrasonography were calculated using SPSS 23.0. Difference in time was calculated as method 1 (ultrasonography) minus method 2 (capnography) and reported as mean with 95% confidence interval; the results were compared using paired student t-test with p values at 95 % level of significance. The analysis was done using SPSS 23.0.

Kappa statistic was used to see agreement over and above that which would have occurred just by chance between these two methods. The kappa (κ) value was calculated using SPSS 23.0. It was interpreted based on the following criteria³⁸:

Table 4. Interpretation of kappa value.³⁸

Kappa value (κ)	Degree of agreement
0.81 - 1.00	Very good.
0.61 - 0.80	Good.
0.41 - 0.60	Moderate.
0.21 - 0.40	Fair.
<0.20	Poor.

[figure not shown]

Fig. 8. Study flow diagram.

(TP=True Positive, FP=False Positive, TN=True Negative, FN=False Negative)

RESULTS

Descriptive data

Demography

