Both ultrasonography and waveform capnography were found to be good, reliable and fairly accurate diagnostic methods of confirming endotracheal tube position. Ultrasonography was comparable diagnostically with capnography for endotracheal tube confirmation. The comparisons of the pretest and posttest probabilities of the two methods are shown in table 10.

Table 10. Comparison of the diagnostic characteristics of ultrasonography and waveform capnography.

	Ultrasonography	Waveform Capnography
Sensitivity in % (95% CI)	97.62 (91.66- 99.71)	96.43 (89.92 - 99.26)
Specificity in % (95% CI)	90.91 (58.72 - 99.77)	100 (71.51 - 100)
PPV in % (95% CI)	98.80 (92.67- 99.81)	100 (100 – 100)
NPV in % (95% CI)	83.33 (55.66 - 95.22)	78.57 (54.69 - 91.76)
Accuracy in % (95% CI)	96.84 (92.92 - 100)	96.84 (92.92 - 100)
Positive likelihood ratio	10.74	Infinity
Negative likelihood ratio	0.03	0.04

(CI= Confidence Interval, PPV= Positive Predictive Value, NPV= Negative Predictive Value)

Both ultrasonography and capnography together had correctly identified 10 out of the 11 oesophageal intubations. The 84 tracheal intubations were correctly identified by both ultrasonography and capnography or either one of these methods. Using the same formula (page 35), the combined accuracy of both the methods together was 98.94% (94 divided by 95, in percentage).

The analysis of agreement between the ultrasonography and capnography results was done using Cohen's kappa statistics. A kappa value of 0.749 with 95% confidence interval of (0.567 – 0.931) and standard error of 0.093 was found. The kappa value therefore showed a good agreement between the result of these two methods.

Time taken for endotracheal tube confirmation

Real-time ultrasonography was faster than waveform capnography for endotracheal tube confirmation in all cases. The mean time for confirmation by ultrasonography was 26.79 ± 7.64 seconds (mean \pm standard deviation). The mean time for confirmation by capnography was 43.03 ± 8.71 seconds.

The mean difference in time was 16.36 seconds (95% CI: 15.70sec – 17.02 sec). The median difference in time was 16 seconds. The standard deviation in difference in time was 3.23 seconds. The standard error of mean (SEM) was 0.332 seconds. The difference in time was highly significant ($p = 0.011$).

Table 11. Time taken for endotracheal tube confirmation.

	Range (in seconds)	Mean \pm SD (in seconds)	Median (in seconds)	IQR (in seconds)	p-value

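### Blinding was visual only: the ultrasound verdict was called aloud before the capnography verdict in all 95 cases, the reference was read after both, and the Limitations do not say so

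*Combined protocol and SAP*

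**What the plan says.** **Blinding.** Materials and Methods describes one safeguard: "the person reading capnogram would face away from the ultrasound machine, and the ultrasound operator would be facing away from the capnograph monitor". Nothing is described that would keep either person from hearing the other.

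**Calls.** In the same section, "The ultrasound operator announced loudly as either" positive (tracheal) or negative (oesophageal). Meanwhile the capnogram reader was watching the monitor, and called a verdict aloud after six mechanical breaths at 26 per minute.

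**Order.** Results, Time taken: "Real-time ultrasonography was faster than waveform capnography for endotracheal tube confirmation in all cases". Table 11 gives a lead of 9 to 24 s, mean 16.36 s.

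**Capnography criterion.** Operational Definitions: "Capnograph positive: meant capnogram showed regular normal shaped waveforms after 6 ventilations"; for the negative, "The capnogram had no waveforms or irregular, bizarre or non-uniform shaped waveforms after 6 ventilations". The proforma in Appendix C adds a count of six positive waves for a tracheal result.

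**Reference.** After both calls, "The supervising anaesthesia faculty then auscultated the chest in 5 areas in the order" that follows. Then: "The ultrasound operator performed bilateral lung ultrasound in second intercostal spaces in the mid-clavicular line and observed for lung sliding". If breath sounds and lung sliding were absent on both sides, laryngoscopy was repeated. The Discussion (Ultrasonography) says it was not repeated when reconfirmation was tracheal.

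**Limitations.** Three items: two capnograph types, several ultrasound operators, no novice operators.

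**The concern.** The report describes blinding and then interprets agreement between two readings as if each had been made without knowledge of the other. In fact a faculty member's verdict was audible to a resident or assistant who had not yet decided. Whether a wave is regular or irregular is a judgement, and the definitions set no number of irregular waves that makes a result negative. The reference was also read by people who had heard or given the index verdicts.

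At stake are kappa, which is a listed objective and underlies the statement of good agreement; the capnography sensitivity and specificity; the equal-reliability conclusion; and the claim that combining the methods improves accuracy. Ultrasound accuracy is exposed only through the reference, because the transtracheal reading came first. The time comparison is little affected, because the capnography end point is set by six ventilations.

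**Working it through.** **1. The lead time, reproduced.** Table 12 gives mainstream n = 37, range 9 to 19 s, mean 14 s; sidestream n = 58, range 12 to 24 s, mean 17.87 s.
- Overall range: 9 to 24 s, as stated.
- Mean: (37 × 14 + 58 × 17.87)/95 = 1554.46/95 = 16.36 s, as stated.
- The minimum is above zero, so the ultrasound verdict was spoken first in 95 of 95 cases.

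**2. How much of the capnogram was still to come.**
- 60/26 = 2.31 s per breath; six breaths = 13.8 s.
- Assume the capnography call came at the sixth breath. At the shortest lead, 9/2.31 = 3.9 breaths remained. The mean lead of 16.36 s exceeds the whole six-breath window.
- If the reader called one breath late, (9 − 2.31)/2.31 = 2.9 breaths remained at the shortest lead. Sidestream sampling delay does not reduce the count: it shifts the display of all waves equally.

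**3. The implied cross-table.** Table 8 (ultrasound): TP 82, FP 1, FN 2, TN 10. Table 9 (capnography): TP 81, FP 0, FN 3, TN 11. The Results say that all 84 tracheal tubes were identified by at least one method, so the 2 and 3 false negatives do not overlap.

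| | Capnography tracheal | Capnography oesophageal |
|---|---|---|
| Ultrasound tracheal | 79 | 4 (3 tracheal tubes, 1 oesophageal) |
| Ultrasound oesophageal | 2 | 10 |

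- Observed agreement = 89/95 = 0.9368.
- Chance agreement = (83 × 81 + 12 × 14)/95² = 0.7635.
- Kappa = (0.9368 − 0.7635)/(1 − 0.7635) = 0.733. The stated value is 0.749, which this table does not reproduce; I start from 0.733.
- Discordant pairs: 4 + 2 = 6 of 95.

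**4. Illustration, not an estimate of bias.** Suppose some agreeing pairs hid a capnography disagreement that was averted by hearing a correct ultrasound verdict. Combined accuracy counts a tube as tracheal if either method says so, which gives the reported 94/95. Each method alone gives 92/95 as reported.

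*Among the 79 both-tracheal pairs (hidden capnography false negatives):*

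| Hidden | Kappa | Capnography sensitivity | Combined |
|---|---|---|---|
| 1 | 0.698 | 80/84 | 94/95 |
| 2 | 0.666 | 79/84 | 94/95 |
| 3 | 0.636 | 78/84 | 94/95 |
| 4 | 0.607 | 77/84 | 94/95 |
| 5 | 0.580 | 76/84 = 90.5% | 94/95 |

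*Among the 10 both-oesophageal pairs (hidden capnography false positives):*

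| Hidden | Kappa | Capnography specificity | Combined |
|---|---|---|---|
| 1 | 0.678 | 10/11 | 93/95 |
| 2 | 0.618 | 9/11 | 92/95 |
| 3 | 0.555 | 8/11 | 91/95 |

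Worked for the last row, table 79/4/5/7: observed 86/95 = 0.9053; chance (83 × 84 + 12 × 11)/95² = 0.7871; kappa 0.555.

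Table 4 puts good at 0.61 to 0.80. At two decimals 0.607 is still good, so on the tracheal side it takes five pairs to leave the band; on the oesophageal side it takes three. Two on the oesophageal side bring the combination down to 92/95, no better than ultrasound alone.

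**The case against.** The strongest reply is that the data speak against copying. Six of 95 pairs were discordant. All three capnography false negatives were called after a spoken positive ultrasound verdict, and the Discussion (Capnography) records more than two irregular waves in each: those readers followed the waveform. The capnogram reader and the reference contradicted all three ultrasound errors, and the reference contradicted all three capnography errors. The six-wave count in the proforma narrows the room for judgement. Reading the reference after the index tests is the normal order, and absent breath sounds with absent lung sliding led to a direct view by laryngoscopy. Finally, inflated capnography accuracy would flatter the comparator, not ultrasound.

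All of this stands, and it limits the likely size. It does not remove the exposure: visible disagreements cannot show how many others were suppressed, and the laryngoscopic check was not applied to tracheal results.

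A reader might infer more than the documents support:
- That readers followed the ultrasound call, or that kappa is inflated by a known amount. The discordant pairs contradict simple copying, and no data allow the effect to be measured.
- That the transtracheal reading was contaminated by capnography. It came first in every case.
- That the faster time for ultrasound is an artefact of the calls. The capnography end point is tied to six breaths.
- That the reference had no objective component. Repeat laryngoscopy supplied one on the oesophageal side.
- In the other direction, that combined accuracy is safe. That holds only if hidden disagreements were all among tracheal tubes.

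**Conclusion.** The point holds as an undisclosed exposure, not as demonstrated bias. It affects 95 of 95 cases, with a lead of 9 to 24 s. Capnography accuracy, kappa and combined accuracy are exposed directly, and ultrasound accuracy only through a reference read with both verdicts known. The likely direction is towards agreement; the size cannot be recovered. The estimates are fragile because the oesophageal cell holds only 10 pairs: three hidden disagreements there would move kappa out of the good band, and two would remove the reported gain from combining.

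This rests on three assumptions: a call made loudly in the same room was heard by the reader; the capnography call came at or near the sixth breath (for the count of breaths remaining); and the cross-table is the one implied by Tables 8 and 9 and the statement on combined identification. The point should be corrected in the report. It does not invalidate the study.

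**What to change.** **Data in hand (text, plus one look through the forms).**
- State in Methods and Limitations, for example: *Blinding was visual only. The ultrasound verdict was audible 9 to 24 seconds before the capnography verdict in every case. The reference was read unblinded after both verdicts, partly by the ultrasound operator. Agreement, capnography accuracy and combined accuracy may be overstated by an unknown amount.*
- Qualify the conclusions on kappa, equal reliability and combined accuracy accordingly.
- Check in the proformas, which list auscultation and lung sliding separately, whether the two ever disagreed. The procedure gives a rule only for findings that agree. Report the count.

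**Any repeat.** In Materials and Methods, replace the spoken ultrasound verdict with a neutral *done* for the stopwatch. At the same moment the operator shows a pre-printed card (trachea or oesophagus) to the researcher and the supervising faculty, out of the capnogram reader's sight, until the capnography verdict is recorded. The supervising faculty sees the result at once and may speak at any time; a tick-box marks such a case as unblinded.

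**Cost.** Two cards, one tick-box and a changed call, with no extra staff. The operator has a small extra task while holding the probe. The scheme protects the capnography reading only: the reference remains unblinded to the ultrasound verdict, and a visible reaction by the supervisor could still give the verdict away.
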